7.5 SECONDARY ENDPOINT ANALYSIS

[figure not shown]
7.5.1 Key secondary endpoint analysis

7.5.1.1 Primary analysis

For the two key secondary efficacy endpoints of change from baseline at Week 26 in SCoRS interviewer total score and VRFCAT adjusted total time T-score, the same strategy for handling the intercurrent events in the primary analysis under the primary estimand will be applied.

The primary analysis will be a restricted maximum likelihood (REML) based approach using the same primary analysis model of MMRM specified in [Section 7.4.1](#), but with the baseline covariate replaced by the baseline of the corresponding key secondary endpoint.

[figure not shown]

7.5.2 (Other) Secondary endpoint analysis

For the secondary efficacy endpoints of change from screening to Week 24 in PRECIS total score and change from baseline to Week 26 in Tower of London number of correct responses T-score, the same strategy for handling the intercurrent events in the primary analysis under the primary estimand will be applied.

For change from screening to Week 24 in PRECIS total score, the primary analysis will be a restricted maximum likelihood (REML) based approach using the same primary analysis model of MMRM specified in [Section 7.4.1](#), but with the baseline covariate replaced by the screening PRECIS total score. The same subgroup analyses as planned for the primary efficacy endpoint in [Section 7.4.3](#) will also be conducted for PRECIS total score.

For change from baseline to Week 26 in the T-score of number of correct responses on Tower of London, an analysis of covariance (ANCOVA) model including treatment, stratification factor of screening MCCB overall composite T-score (<30, ≥ 30), and baseline number of correct responses on Tower of London T-score will be fitted to the data.

7.7 EXTENT OF EXPOSURE

Extent of exposure will be summarized for the treated set using descriptive statistics for days on treatment as well as frequency and percentage of subjects in the following categories: <42, 42 - <84, 84 - <126, 126 - <168, 168 - <179, 179 - <190, ≥ 190 .

7.8 SAFETY ANALYSIS

All safety analyses will be performed on the treated set and other subject sets as appropriate.

7.8.1 Adverse events

Unless otherwise specified, the analyses of AEs will be descriptive in nature. All analyses of AEs will be based on the number of subjects with AEs and not on the number of AEs. The reporting and analyses of AEs will follow the BI guideline (3). AEs will be coded with the most current version of MedDRA®.

For further details on summarization of AE data, please refer to (1, 3).

The analysis of AEs will be based on the concept of treatment emergent AEs. That means that all AEs occurring between the date of the first administration of trial treatment till the date of the last administration of trial treatment + residual effect period will be assigned to the on-treatment period. All AEs occurring before the first administration of trial treatment will be assigned to 'screening' and all AEs occurring after the residual effect period will be assigned to 'follow-up'. For details on the treatment definition, see [Section 6.1](#).

Adverse events of special interest (AESIs)

A hepatic injury is defined by the following alterations of hepatic laboratory parameters:

- an elevation of AST and / or ALT ≥ 3 fold ULN combined with an elevation of total bilirubin ≥ 2 fold ULN measured in the same blood draw sample; and / or
- marked peak aminotransferase (ALT and / or AST) elevations ≥ 10 fold ULN.

See CTP Section 5.2.6.1.

Other significant AEs

User-defined AE category	MedDRA preferred terms	
Drug abuse, dependence, withdrawal and substance-related disorders, including diversion	Accidental death	Intentional overdose
	Drug abuse	Muscle rigidity
	Accidental overdose	Nasal necrosis
	Accidental poisoning	Nasal septum perforation
	Dependence	Nasal septum ulceration
	Drug abuser	Needle track marks
	Product administered at inappropriate site	Neonatal complications of substance abuse
	Drug dependence	Overdose
	Drug detoxification	Poisoning
	Drug dependence antepartum	Poisoning deliberate
	Drug dependence, postpartum	Substance dependence
	Drug diversion	Prescription form tampering
	Drug tolerance	Product tampering
	Drug tolerance increased	Product used for unknown indication
	Toxicity to various agents	Rebound effect
	Drug use disorder	Seizure
	Drug use disorder antepartum	Status epilepticus
	Drug use disorder, postpartum	Substance abuse
	Drug withdrawal convulsions	Substance abuser
	Drug withdrawal headache	Substance use
	Drug withdrawal syndrome	Substance use disorder
	Drug withdrawal syndrome neonatal	Substance-induced mood disorder
	Generalised tonic-clonic seizure	Substance-induced psychotic disorder
	Hangover	Treatment noncompliance
	Intentional product misuse	Withdrawal syndrome
Euphoria-related adverse events	Dizziness	Feeling drunk
	Euphoric mood	Feeling of relaxation
	Feeling abnormal	Inappropriate affect
CNS depressant effects	Depressed level of consciousness	Sedation
	Fatigue	Sluggishness
	Hypersomnia	Somnolence
	Lethargy	Stupor
	Loss of consciousness	
Stimulation and anxiety-related adverse events	Agitation	Morbid thoughts
	Anxiety	Nervousness
	Anxiety disorder	Panic attack
	Anticipatory anxiety	Panic disorder
	Energy increased	Panic reaction
	Fear	Psychogenic tremor

	Fear of death	Psychomotor hyperactivity
	Feeling jittery	Restlessness
	Generalised anxiety disorder	Tension
	Hypervigilance	
Perceptual disturbances / psychotomimetic effects	Abnormal dreams	Hypoesthesia
	Acute psychosis	Ideas of reference
	Aggression	Illogical thinking
	Alice in wonderland syndrome	Illusion
	Altered state of consciousness	Incoherent
	Altered visual depth perception	Indifference
	Anger	Jamais vu
	Communication disorder	Loose associations
	Confusional state	Magical thinking
	Consciousness fluctuating	Nightmare
	Déjà vu	Paranoia
	Delirium	Paroxysmal perceptual alteration
	Delusion	Psychotic behaviour
	Delusion of grandeur	Psychotic disorder
	Delusion of reference	Psychotic symptom
	Delusion of replacement	Reactive psychosis
	Delusional perception	Rebound psychosis
	Derailment	Sensory disturbance
	Disinhibition	Sensory level abnormal
	Disorientation	Slow speech
	Dysarthria	Somatic delusion
	Flight of ideas	Somatic hallucination
	Formication	Staring
	Hallucination	Suspiciousness
	Hallucination, auditory	Tangentiality
	Hallucination, gustatory	Thinking abnormal
	Hallucination, olfactory	Thought blocking
	Hallucination, synaesthetic	Thought broadcasting
	Hallucination, tactile	Thought insertion
	Hallucination, visual	Thought withdrawal
	Hallucinations, mixed	Transient psychosis
	Hostility	
Dissociation	Daydreaming	Hypogeusia
	Depersonalisation/derealisation disorder	Metamorphopsia
	Derealisation	Ocular discomfort
	Diplopia	Oral dysaesthesia
	Dissociation	Oral hyperesthesia

	Dissociative disorder	Pain threshold decreased
	Dissociative identity disorder	Paraesthesia
	Dysaesthesia	Paraesthesia oral
	Dysaesthesia pharynx	Pharyngeal hypoesthesia
	Dysgeusia	Pharyngeal paraesthesia
	Dysmetropsia	Photophobia
	Feeling cold	Photopsia
	Feeling hot	Synaesthesia
	Feeling of body temperature change	Time perception altered
	Flashback	Tinnitus
	Hyperacusis	Vision blurred
	Hyperaesthesia	Visual impairment
	Hypersensitivity	
Mood disorders and disturbances	Abnormal behaviour	Depressive delusion
	Affect lability	Depressive symptom
	Affective disorder	Disturbance in social behaviour
	Anhedonia	Emotional disorder
	Antisocial behaviour	Emotional distress
	Apathy	Feeling of despair
	Asocial behaviour	Flat affect
	Attention-seeking behaviour	Hypomania
	Belligerence	Impatience
	Blunted affect	Impulse-control disorder
	Compulsive cheek biting	Impulsive behaviour
	Compulsive handwashing	Irritability
	Compulsive hoarding	Mania
	Compulsive lip biting	Mood altered
	Compulsive sexual behaviour	Mood swings
	Compulsive shopping	Parasomnia
	Obsessive-compulsive symptom	Personality change
	Compulsions	Sleep talking
	Confusional arousal	Sleep terror
	Depressed mood	Sleep-related eating disorder
	Depression	Somnambulism
Mental and cognitive impairment	Amnesia	Impaired driving ability
	Amnestic disorder	Impaired reasoning
	Anterograde amnesia	Judgement impaired
	Balance disorder	Memory impairment
	Bradyphrenia	Mental disability
	Change in sustained attention	Mental disorder
	Cognitive disorder	Mental impairment
	Confabulation	Mental status changes

Coordination abnormal	Paramnesia
Distractibility	Psychomotor retardation
Disturbance in attention	Psychomotor skills impaired
Dyslogia	Retrograde amnesia
Executive dysfunction	Transient global amnesia

According to ICH E3, in addition to deaths and serious adverse events, ‘other significant’ AEs need to be listed in the clinical trial report. These will include:

1. Any adverse events that led to an intervention, such as withdrawal of drug treatment.
2. Marked haematological and other lab abnormalities or lead to significant concomitant therapy as identified by the Clinical Monitor/Investigator during medical quality review at TOM.

AEs suggestive of abuse potential or related to CNS depressant effects

In support of an evaluation of human abuse potential, user-defined AE categories (UDAEC) are defined in [Table 7.8.1: 1](#) for AEs suggestive of abuse potential and AEs related to CNS depressant effects.

Table 7.8.1: 1 MedDRA preferred terms for user-defined AE categories of AEs suggestive of abuse potential or related to CNS depressant effects

Other UDAECs are defined as follow:

Ocular events

The grouping of “ocular events” includes all MedDRA preferred terms under the SOC of “eye disorder” regardless of primary or secondary SOC.

Anaemia

Anaemia will be analyzed by BI customized medical query (BIcMQ) of Decreased haemoglobin and anaemia (incl. non-haematological causes), as defined in [Table 7.8.1: 2](#)

In addition, Standardised MedDRA Query (SMQ) of Haematopoietic cytopenias will be analyzed.

Table 7.8.1: 2 MedDRA preferred terms for BIcMQ of Decreased haemoglobin and anaemia (incl. non-haematological causes)

User-defined AE category	MedDRA preferred terms	
Decreased haemoglobin and anaemia (incl. non-haematological causes)	Anaemia	Haemoglobin abnormal
	Anaemia Heinz body	Haemoglobin decreased
	Anaemia folate deficiency	Haemolytic anaemia
	Anaemia macrocytic	Haemolytic anaemia enzyme specific
	Anaemia megaloblastic	Haemolytic icterohaemorrhagic anaemia
	Anaemia of chronic disease	Hyperchromic anaemia
	Anaemia of malignant disease	Hypochromic anaemia

Anaemia postoperative	Hypoplastic anaemia
Anaemia splenic	Iron deficiency anaemia
Anaemia vitamin B12 deficiency	Leukoerythroblastic anaemia
Anaemia vitamin B6 deficiency	Macrocytosis
Anaemic hypoxia	Melanaemia
Anaemic retinopathy	Microangiopathic haemolytic anaemia
Aplasia pure red cell	Microcytic anaemia
Aplastic anaemia	Nephrogenic anaemia
Autoimmune anaemia	Normochromic anaemia
Autoimmune aplastic anaemia	Normochromic normocytic anaemia
Autoimmune haemolytic anaemia	Normocytic anaemia
Blood loss anaemia	Pernicious anaemia
Cardiac haemolytic anaemia	Proerythroblast count abnormal
Cold type haemolytic anaemia	Proerythroblast count decreased
Coombs negative haemolytic anaemia	Protein deficiency anaemia
Coombs positive haemolytic anaemia	Radiation anaemia
Copper deficiency anaemia	Red blood cell abnormality
Deficiency anaemia	Red blood cell count abnormal
Dilutional anaemia	Red blood cell count decreased
Erythroblast count abnormal	Reticulocyte count abnormal
Erythroblast count decreased	Reticulocyte count decreased
Erythroid dysplasia	Reticulocyte percentage decreased
Erythroid maturation arrest	Reticulocytopenia
Erythropenia	Scorbutic anaemia
Erythropoiesis abnormal	Sideroblastic anaemia
Erythropoietin deficiency anaemia	Spherocytic anaemia
Haematocrit abnormal	Spur cell anaemia
Haematocrit decreased	Warm autoimmune haemolytic anaemia

Drowsiness

Drowsiness will be analyzed by a customized query defined in [Table 7.8.1: 3](#).

Table 7.8.1: 3 MedDRA preferred terms for user-defined AE category of Drowsiness

User-defined AE category	MedDRA preferred terms	Scope
Drowsiness	Depressed level of consciousness	Narrow

	Post-injection delirium sedation syndrome	Narrow
	Radiation somnolence syndrome	Narrow
	Sedation	Narrow
	Altered state of consciousness	Broad
	Brain fog	Broad
	Concussion	Broad
	Consciousness fluctuating	Broad
	Intracranial hypotension	Broad
	Lethargy	Broad
	Obstructive sleep apnoea syndrome	Broad
	Orexin deficiency	Broad
	Pickwickian syndrome	Broad
	Post concussion syndrome	Broad
	Presyncope	Broad
	Sedation complication	Broad
	Sleep-related hypoventilation	Broad
	Shift work disorder	Broad
	Sleep apnoea syndrome	Broad

Sleep disorder

Sleep disorder related AE search terms are based upon the FDA Medical Queries (FMQs) of Insomnia (broad) and Somnolence (broad). Refer to [Table 7.8.1: 4](#) for a list of MedDRA preferred terms in each of the groupings.

Table 7.8.1: 4 MedDRA preferred terms for user-defined AE categories of sleep disorder AEs

User-defined AE category	MedDRA preferred terms	
FMQ Insomnia (broad)	Advanced sleep phase	Primary insomnia
	Behavioural induced insufficient sleep syndrome	Psychophysiologic insomnia
	Circadian rhythm sleep disorder	Shift work disorder
	Delayed sleep phase	Sleep disorder due to general medical condition, insomnia type
	Dyssomnia	Sleep disorder due to general medical condition, mixed type
	Early morning awakening	Terminal insomnia
	Fatal familial insomnia	Dysfunctions associated with sleep stages or arousal from sleep
	Hyposomnia	Dyssomnia NOS
	Initial insomnia	Jet lag
	Insomnia	Microsleep
	Insomnia exacerbated	Sleep deficit
	Insomnia NEC	Sleep disorder
	Insomnia related to another mental condition	Sleep disorder due to a general medical condition
	Irregular sleep phase	Sleep disorder NOS
	Irregular sleep wake rhythm disorder	Sleep disorder therapy

	Middle insomnia	Sleep inertia
	Non-24-hour sleep-wake disorder	Sleep study abnormal
	Poor quality sleep	
FMQ Somnolence (broad)	Central nervous system depression NOS	Sedation aggravated
	Consciousness fluctuating	Somnolence
	Depressed level of consciousness	Somnolence neonatal
	Hypersomnia	Stupor
	Infant sedation	Altered state of consciousness
	Lethargy	Fatigue
	Neonatal oversedation	Fatigue aggravated
	Primary hypersomnia	Prostration
	Sedation	Sluggishness

An overall summary of adverse events will be presented, including frequency of schizophrenia relapse. The frequency of subjects with AEs will be summarised by treatment, primary system organ class (SOC) and preferred term (PT). The SOCs will be sorted by default in descending frequency and PTs will be sorted in descending frequency within an SOC in the iclepirtin arm. Separate tables will be provided for patients with

- Related AEs
- Serious AEs
- Serious related AEs
- AESIs
- Other significant AEs
- AEs leading to death
- AE leading to discontinuation of trial medication
- AEs occurred with incidence in the preferred term >2%
- AEs suggestive of abuse potential or related to CNS depressant effects
- AEs in user-defined AE categories
- AEs occurred during the follow-up period.

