#### 1.2.4 Clinical Pharmacology

Iclepertin has a half-life ranging from 37 to 59 h. Steady state is reached after 6 days of dosing with accumulation ratios for Cmax ranging from 1.96 to 2.63 and for AUC from 2.31 to 3.21. In the single rising dose study 1346.1 ([c02820512](#)) at 25 mg dose the effect of a high calorie, high fat meal resulted in an increased exposure with fed/faasted ratio for Cmax 142% and for AUC0-tz 126%. The multiple rising dose study 1346.2 ([c03572014](#)) looked at the effect of a light meal, and the effect is much less pronounced. In phase II, patients were allowed to take Iclepertin "with or without" food as no clinically relevant effect on exposure was expected. In Phase III 10mg Iclepertin will also be administered with or without food as the expected increase of exposure is below the exposure already observed in previous trials, e.g. 1346-0009 ([c31477880](#)).

As the mechanism of action involves enhancement of brain plasticity (which is higher during day than during night), dosing should occur after waking up (i.e. preferably in the morning). Pharmacokinetic parameters between young and elderly healthy subjects, and between Japanese, Chinese and Caucasian subjects are comparable.

Iclepertin crosses blood-brain barrier and the required 50% glycine increase in the CSF was observed after multiple dosing of 10 mg Iclepertin.

Iclepertin is a sensitive substrate of CYP3A4, and co-administration of moderate to strong CYP3A4 inducers / inhibitors is not permitted, as this reduces / increases plasma concentrations of Iclepertin. CYP3A4 sensitive drugs with narrow therapeutic index (NTI) are restricted during the treatment period. For CYP3A4 sensitive drugs without NTI investigators should assess if dose adjustments and/or monitoring of the underlying disease is clinically required for patients who are taking such drugs. List of prohibited medication is inserted in the ISF, although the impact on common comedication in this target population is minimal. Details can be found in Investigator Brochure that is updated and provided to sites at regular intervals.

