| Placebo Risks  | 

There is currently no approved medication indicated for treatment of CIAS. Since an approved, effective comparator is not available for this study, a placebo control group is being used in this study design.

According to the medication assignment planned in this trial, patients will be assigned to placebo or Iclepertin arm 10 mg in 1:1 ratio.

 | 

Inclusion criteria require that patients enrolled in this clinical trial should be clinically stable and on stable SoC treatment with antipsychotic and other psychotropic medications.

Maintenance antipsychotic treatment is needed to prevent relapse of acute psychotic episode. Thus, assignment to the placebo arm or stopping the study drug during the treatment period is not associated with a higher risk of psychotic relapse.

Psychiatric events, positive and negative symptoms, and suicidality will be monitored throughout the study to ensure that worsening of pre-existing conditions or any newly occurring events are detected and any necessary actions taken according to stopping criteria.

 |
| Risks of stopping study drug                               | In the Phase II study, following end-of-treatment, no increases in adverse events were observed in patients treated with Iclepertin in comparison to those treated with placebo. Potential adverse events after stopping study drug have not been formally investigated thus far and therefore cannot be fully excluded.   | 

Monitoring AEs of interest for assessment of potential abuse liability are described above (refer to placebo risks).

In one of the Phase III studies (c33087946), after completion of 26 weeks of treatment, all patients will be closely monitored during the 4 weeks in the safety follow up period to assess potential adverse events of withdrawal from Iclepertin treatment.

  |

Table 1.4.2:1 Overview over trial related risks (con't)

| Possible/ known risks of clinical relevance for this trial | Summary of data, rationale for the risk   | • Mitigation strategy   |
|--|---|---|
| Trial procedures                                    |   |   |

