#### **5.2.6.6 Monitoring of adverse events after stopping of study medication**

Patients who are not rolling over to the extension trial should be closely monitored during the safety follow up period to assess AEs after stopping of study medication.

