6. GENERAL ANALYSIS DEFINITIONS

6.1 TREATMENT(S)

For basic study information on treatments to be administered, assignment of treatment groups, select of doses, see CTP Section 4.

Table 6.1: 1 lists the two treatment groups in this study. Table 6.1: 2 defines the analysing treatment period for safety analyses. For this study, the residual effect period (REP) is defined as 12 days after the last dose of trial medication.

Table 6.1: 1 Treatment descriptions

Long Name	Short Name
Placebo	Placebo
Iclepertin 10 mg QD	Iclepertin 10 mg

Table 6.1: 2 Analysing treatment periods (same for all treatment groups)

Analysing Treatment Period	Start Date	End Date
Screening period	Date of informed consent	Date of the first treatment administration – 1 day
On-treatment period	Date of the first treatment administration	Date of the last treatment administration + REP
Post-treatment period	Date of the last treatment administration + REP + 1 day	Date of the last per protocol visit

REP is the residual effect period which is defined as 12 days after the last dose of trial treatment.

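### The visible SAP has no analysis that separates adverse events in days 1–12 after the last dose, so early non-specific withdrawal events are pooled with on-drug events

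*SAP*

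**What the plan says.** **How the SAP divides time.** SAP 6.1 states that "REP is the residual effect period which is defined as 12 days after the last dose of trial treatment", and Table 6.1: 2 starts the post-treatment period at "Date of the last treatment administration + REP + 1 day". SAP 7.8.1 applies this to AEs. Those from the first dose "till the date of the last administration of trial treatment + residual effect period will be assigned to the on-treatment period", while "all AEs occurring after the residual effect period will be assigned to" follow-up. The list of AE tables at the end of SAP 7.8.1 has one entry tied to the off-drug period: "AEs occurred during the follow-up period". AE analyses count subjects with an event, not events.

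**What the protocol asks for.** Protocol 5.2.6.6 says that patients who do not roll over "should be closely monitored during the safety follow up period to assess AEs after stopping of study medication". Flow-chart footnote 15 refers to that section and describes it as monitoring for withdrawal AEs. Table 1.4.2:1 gives the background: "Potential adverse events after stopping study drug have not been formally investigated thus far".

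**Drug kinetics.** Protocol 1.2.4: "Iclepertin has a half-life ranging from 37 to 59 h". Protocol 3.2 puts elimination at about 12 days and uses this to justify the 28-day follow-up.

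**The concern.** After the last dose the SAP recognises two AE periods, and the boundary falls roughly where elimination is complete. An event on day 3 after stopping is counted together with events from 26 weeks on drug. The table that a reader would consult for withdrawal effects begins once the drug has nearly gone.

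An early rise in anxiety, insomnia or headache in patients who stopped iclepertin would then be diluted in the on-treatment tables and absent from the follow-up table. Because subjects are counted rather than events, a patient who had headache on drug and again after stopping adds nothing to the on-treatment headache count. A clean follow-up table could be read as evidence of no withdrawal effect although the washout days were never examined separately.

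**Working it through.** **1. The plan's 12 days.** The documents give no formula for the residual effect period. Assuming five times the longest half-life: 5 × 59 h ÷ 24 = 12.3 days, against 12 stated. The figure is consistent with a conventional washout rule.

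**2. Drug remaining by day after the last dose.** Inputs: half-life 37–59 h (Protocol 1.2.4). Assumption: first-order elimination, so the fraction left after d days is 0.5^(24d ÷ half-life).

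| Day after last dose | Half-life 37 h | Half-life 59 h |
|---|---|---|
| 3 | 26.0% | 42.9% |
| 7 | 4.3% | 13.9% |
| 12 | 0.45% | 3.4% |

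Twelve days is 288 h, which is 288 ÷ 59 = 4.9 to 288 ÷ 37 = 7.8 half-lives. Between 96.6% and 99.5% of the decline lies inside the window labelled on-treatment.

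**3. Days covered for a completer who does not roll over.** Inputs: end-of-treatment visit on day 183 (flow chart); last dose the day before, day 182 (Protocol 4.1.4); Follow-up 2 at 28 days, day 211, window +7 days.

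- Residual effect period ends: 182 + 12 = day 194.
- Off-drug days to Follow-up 2: 211 − 182 = 29 (36 with the window).
- Days in the SAP's follow-up period: 211 − 194 = 17 (24 with the window).
- Share of off-drug time labelled on-treatment: 12 ÷ 29 = 41% (12 ÷ 36 = 33%).
- Share of the on-treatment window that is off drug: 12 ÷ 194 = 6.2%.

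The last figure shows the dilution: an early cluster occupies about one sixteenth of the window in which it is counted.

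**4. Patients concerned.** Protocol 7.5 projects that 30–40% will stop treatment early. With 293 per arm and equal stopping assumed: 0.30 × 293 = 88 and 0.40 × 293 = 117 on iclepertin. This is an upper bound, because some will withdraw consent and some may restart drug. Completers who do not roll over come on top; the documents do not project their number.

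**5. Where an event would appear in the visible tables.**

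| Event | Planned output |
|---|---|
| Coded to a withdrawal or rebound term, any time | Abuse-potential category table, with no split by time since last dose |
| Any term, onset day 13 or later | Follow-up table |
| Non-specific term, onset days 1–12 | On-treatment tables, not separable from on-drug events |

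The third row is the gap.

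**The case against.** The case for leaving the SAP as it is has real substance.

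- **The rule is the protocol's own.** Protocol 7.2.5 defines treatment-emergent in the same way, and Protocol 1.2.2 explains why: drug or its effects may still be present for 12 days. A reader might infer that the SAP departs from the protocol or that the 12-day rule is an error. Neither is so.
- **Withdrawal events are not lost.** SAP Table 7.8.1: 1 includes drug withdrawal syndrome, drug withdrawal headache, withdrawal syndrome and rebound effect, in a category that has its own table. Later events reach the follow-up table. To say that the plan cannot show withdrawal events would therefore be too strong.
- **The main withdrawal assessment lies elsewhere.** The mitigation column of Protocol Table 1.4.2:1 assigns close monitoring of all patients after treatment to another Phase III trial, identified in the reference list as 1346-0012. The same table reports no increase in AEs after end of treatment relative to placebo in Phase II. In this trial completers are encouraged to roll over at the end-of-treatment visit, which removes their off-drug period.
- **Timing is assumed.** Nothing in the documents says that withdrawal events cluster during washout. Some could come later, where the follow-up table would capture them.
- **Not everything is visible.** Parts of the SAP are redacted, and AE reporting also follows a sponsor guideline that is not available.

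All of this stands and narrows the point. None of it supplies a visible analysis by time since last dose. The assignment to 1346-0012 does not cancel Protocol 5.2.6.6 or footnote 15, and does not cover patients who stop early in this trial.

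**Conclusion.** The point holds as a gap in reporting. The visible SAP does not isolate AEs with onset in days 1–12 after the last dose, the period in which about 96.6–99.5% of the drug is eliminated, and early non-specific events are pooled with on-drug events. For a completer who does not roll over, 12 of 29 off-drug days are affected.

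The conclusion rests on first-order elimination at the stated half-lives and on the visible SAP text being complete on this matter. Its practical weight also depends on withdrawal events tending to occur during washout, which is an assumption.

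Two larger claims are tempting and not supported. One is that the rule materially inflates the on-drug safety profile: the 12 days are 6.2% of a completer's window, and the same rule applies to both arms. The other is to count every projected early stopper, 176–234 of 586, as at risk: that covers both arms, and placebo patients cannot have iclepertin withdrawal. No efficacy conclusion is touched.

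**What to change.** Leave the treatment-emergent definition unchanged and add to SAP 7.8.1:

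- a descriptive by-arm table of AEs with onset from the day after the last dose to Follow-up 2, split at day 12, in patients who stop early or do not roll over, censored at restart of trial drug or at the first dose in the extension trial;
- the abuse and withdrawal term categories of Table 7.8.1: 1 on the same window and split.

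State with the table that this subset is selected after randomisation, so that differences between arms are descriptive only; that some events will appear in two tables; and that the timing of withdrawal events within washout is an assumption.

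The cost is a short paragraph and one or two tables from dates already collected, with no new data. If a redacted SAP section or the sponsor's AE guideline already specifies such a table, a cross-reference in SAP 7.8.1 is sufficient.
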